4.6 PATIENT, TREATMENT, STUDY, AND SITE DISCONTINUATION

4.6.1 Patient Discontinuation

Patients have the right to voluntarily withdraw from the study at any time for any reason. In addition, the investigator has the right to withdraw a patient from the study at any time. Reasons for withdrawal from the study may include, but are not limited to, the following:

- Patient withdrawal of consent at any time
- Any medical condition that the investigator or Sponsor determines may jeopardize the patient's safety if he or she continues in the study
- Investigator or Sponsor determines it is in the best interest of the patient
- Patient non-compliance with protocol procedures

Every effort should be made to obtain information on patients who withdraw from the study. The primary reason for withdrawal from the study should be documented on the appropriate eCRF. However, patients will not be followed for any reason after consent has been withdrawn. Patients who withdraw from the study will not be replaced.

4.6.2 Study Treatment Discontinuation

Patients must discontinue study treatment and not receive repeat treatment if they experience any of the following:

- Pregnancy
- Progressive multifocal leukoencephalopathy (PML)
- Malignant events (except basal cell carcinoma and squamous cell carcinoma of the skin that have been excised and cured)
- Stevens-Johnson syndrome (SJS)/toxic epidermal necrolysis (TEN)
- Severe allergic or anaphylactic study drug treatment-related reaction
- National Cancer Institute Common Terminology Criteria for Adverse Events (NCI CTCAE) Grade 4 (life-threatening) event during or within 24 hours of an infusion
- Pure red cell aplasia

The primary reason for study treatment discontinuation should be documented on the appropriate eCRF. Patients who discontinue study treatment prematurely will not be replaced.

In the event that the patient develops a medically significant NCI CTCAE Grade 3 or 4 infection, see Section [4.6.4](#).

Rituximab—F. Hoffmann-La Roche Ltd
58/Protocol WA29330, Version 5

4.6.3 Study and Site Discontinuation

The Sponsor has the right to terminate this study at any time. Reasons for terminating the study may include, but are not limited to, the following:

- The incidence or severity of adverse events in this or other studies indicates a potential health hazard to patients.
- Patient enrollment is unsatisfactory.

The Sponsor will notify the investigator if the Sponsor decides to discontinue the study.

The Sponsor has the right to close a site at any time. Reasons for closing a site may include, but are not limited to, the following:

- Excessively slow recruitment
- Poor protocol adherence
- Inaccurate or incomplete data recording
- Non-compliance with the International *Council for* Harmonisation (ICH) guideline for Good Clinical Practice
- No study activity (i.e., all patients have completed and all obligations have been fulfilled)

4.6.4 Dose Modification and Treatment Interruption

In the event that the patient develops a medically significant NCI CTCAE Grade 3 or 4 infection, no further doses of rituximab/placebo or MMF/placebo study drug treatment should be provided until the infection has resolved.

Rituximab and matching placebo: Prolonged B-cell depletion is the expected outcome of rituximab treatment and is not considered a toxicity.

Patients who experience a Grade 4 (life-threatening) event during an infusion of rituximab (or matching placebo) should have their infusion stopped. Additional infusions of rituximab (or matching placebo) should not be given.

MMF and matching placebo: During the 52-week treatment period, the MMF (or matching placebo) dose should remain as stable as possible. If reductions in dose are necessary because of tolerability, decreases will be allowed in 500-mg decrements and must be recorded on the appropriate eCRF. If neutropenia develops ($ANC < 1.3 \times 10^3/\mu L$), dosing with MMF (or matching placebo) should be interrupted or the dose should be reduced.

Guidelines for dosage modification and treatment interruption or discontinuation of MMF are provided in the MMF prescribing information.

Rituximab—F. Hoffmann-La Roche Ltd
59/Protocol WA29330, Version 5

In addition to the above, the following safety criteria must be met prior to resuming either rituximab/placebo or MMF/placebo study drug treatment:

- ANC $\geq 1.3 \times 10^3/\mu\text{L}$ at the last blood sample analysis
- The patient has not developed any of the following:
 - Primary or secondary immunodeficiency, including HIV infection
 - Known active infection of any kind (excluding fungal infections of nail beds), or any major episode of infection requiring hospitalization or treatment with IV anti-infectives within 4 weeks prior to infusion or within 2 weeks prior to oral MMF (matching placebo) and completion of oral anti-infectives within 2 weeks prior to infusion or within 1 week prior to oral MMF (matching placebo)
 - The patient has not developed any conditions that, in the investigator's opinion, would preclude the patient from receiving further courses of treatment, such as: any new or uncontrolled disease including, but not limited to, cardiovascular disease; nervous system, pulmonary, renal, hepatic, endocrine, or gastrointestinal disorders; or malignancies
- Patient is not pregnant or breastfeeding

5. ASSESSMENT OF SAFETY

5.1 SAFETY PLAN

Patient safety will be monitored through physical examination, regular assessment of vital signs, hematologic laboratory tests, and incidence and severity of adverse events potentially due to any of the study medications. Infections will be treated according to local standard of care. Corticosteroid-related adverse events will also be assessed. An iDMC will review all safety data during the course of the study (see Section 3.1.4).

Given the known side effects of both rituximab and MMF, abnormalities in hematologic tests, specifically leukocyte count, hemoglobin, and platelet count will be monitored closely. If the patient becomes leukopenic or thrombocytopenic, or experiences intolerable gastrointestinal adverse effects, the dose of MMF or dosing schedule of rituximab will be altered at the investigator's discretion.

5.1.1 Side Effects Known to be Associated with Rituximab

5.1.1.1 Infusion-Related Reactions

Rituximab is associated with infusion-related reactions, which may be related to release of cytokines and/or other chemical mediators.

For RA patients, most infusion-related events reported in clinical trials were mild to moderate in severity. Severe infusion-related reactions with fatal outcomes have been rarely reported in the postmarketing setting. Closely monitor patients with preexisting cardiac conditions and those who experienced prior cardiopulmonary adverse reactions. The most common symptoms were headache, pruritus, throat irritation, flushing, rash, urticaria, hypertension, and pyrexia. In general, the proportion of patients experiencing any infusion-related reaction was higher following the first infusion of any treatment

Rituximab—F. Hoffmann-La Roche Ltd
60/Protocol WA29330, Version 5

course than following the second infusion. Subsequent rituximab infusions were better tolerated by patients than the initial infusion. Fewer than 1% of patients experienced serious infusion-related reactions, with most of these reported during the first infusion of the first course. The reactions reported were usually reversible with a reduction in rate or interruption of rituximab infusion, and administration of an anti-pyretic, an antihistamine, and, occasionally, oxygen, IV saline, bronchodilators, or glucocorticoids, as required.

Anaphylactic and other hypersensitivity reactions have been reported following the IV administration of proteins to patients. Medicinal products for the treatment of hypersensitivity reactions, e.g., epinephrine, antihistamines, and glucocorticoids, should be available for immediate use in the event of an allergic reaction during administration of rituximab.

Infusion-related reactions in patients with GPA and MPA were similar to those seen in RA patients in clinical trials. For patients with GPA and MPA, rituximab was given in combination with high doses of glucocorticoids, which may reduce the incidence and severity of these events.

Patients with a history of a severe allergic or anaphylactic reaction to humanized or murine monoclonal antibodies, or known hypersensitivity to any component of rituximab, will be excluded from study participation.

On rituximab infusion days, vital signs will be collected immediately prior to infusion and then every 30 minutes until the end of the infusion. To reduce the frequency and severity of infusion-related reactions, patients will receive premedication prior to the start of each infusion of rituximab or rituximab placebo (see Section 4.3.2.1 and Appendix 3).

5.1.1.2 Cardiovascular Events

Since hypotension may occur during rituximab infusion, consideration should be given to withholding anti-hypertensive medications 12 hours prior to the rituximab/matching placebo infusion. Angina pectoris, cardiac arrhythmias such as atrial flutter and fibrillation, heart failure, or myocardial infarction have occurred in patients treated with rituximab. Therefore, patients with a history of cardiac disease should be monitored closely, especially during infusions (see Section 5.1.1.1).

5.1.1.3 Infection

Patients may have an increased risk of infection following rituximab therapy. Rituximab should not be administered to patients with an active infection or to patients who are severely immunocompromised (e.g., where levels of CD4+ or CD8+ cell counts are very low).

Physicians should exercise caution when considering the use of rituximab in patients with a history of recurring or chronic infections or with underlying conditions that may

Rituximab—F. Hoffmann-La Roche Ltd
61/Protocol WA29330, Version 5

further predispose patients to serious infection. Patients with a history of or currently active primary or secondary immunodeficiency, including known history of HIV infection, will be excluded from study participation. Patients with a known active infection of any kind (excluding fungal infections of nail beds) or any major episode of infection requiring hospitalization or treatment with IV anti-infectives within 4 weeks prior to screening, or completion of oral anti-infectives within 2 weeks prior to randomization, will also be excluded.

Patients who develop infection following rituximab therapy should be promptly evaluated and treated appropriately. Repeat infusions of rituximab (or matching placebo) should only be considered once any infection has fully resolved (see Section 4.6.4).

5.1.1.4 Hepatitis B Infection

Cases of hepatitis B virus (HBV) reactivation, including those with a fatal outcome, have been reported in RA, GPA, and MPA patients receiving rituximab. HBV screening should always be performed in high-risk patients before initiation of treatment with rituximab. Carriers of hepatitis B and patients with a history of hepatitis B should be closely monitored for clinical and laboratory signs of active HBV infection during and for several months following rituximab therapy.

Patients will be tested for HBsAg, HBcAb, and HCV serology at screening. Those testing positive will be excluded from study participation.

5.1.1.5 Progressive Multifocal Leukoencephalopathy

Very rare cases of fatal PML have been reported following use of rituximab for the treatment of autoimmune diseases, including RA. Several, but not all, of the reported cases had potential risk factors for PML, including the underlying disease, long-term immunosuppressive therapy, or chemotherapy. PML has also been reported in patients with autoimmune disease not treated with rituximab. Physicians treating patients with autoimmune diseases should consider PML in the differential diagnosis of patients reporting neurological symptoms, and consultation with a neurologist should be considered as clinically indicated, including further evaluation with magnetic resonance imaging (MRI; preferably with contrast), cerebrospinal fluid testing for JC viral DNA, and repeat neurological assessments.

If PML is diagnosed in a patient receiving rituximab, no additional infusions of rituximab should be administered; reductions in concomitant immunosuppressive therapy and appropriate treatment, including antiviral therapy, should be considered. There are no known interventions that can reliably prevent PML or adequately treat PML, should it occur.

At the time of initiation of this protocol, there were no reports in the literature or in the Sponsor's global safety database of PML in PV patients who have received rituximab.

Rituximab—F. Hoffmann-La Roche Ltd
62/Protocol WA29330, Version 5

5.1.1.6 Skin Reactions

Severe skin reactions, such as SJS and TEN, some with fatal outcome, have been reported. In case of such an event with a suspected relationship to rituximab, treatment should be permanently discontinued.

Additional information on side effects associated with rituximab is provided in the Investigator's Brochure.

5.1.1.7 Immunization

The safety of immunization with live viral vaccines following rituximab therapy has not been studied. Therefore, vaccination with live viral vaccines is not recommended while on rituximab or while peripheral B cells are depleted. It is recommended that a patient's vaccination status be reviewed and current immunization guidelines followed prior to study entry. Should non-live vaccinations be required, immunization should be completed at least 4 weeks prior to the first administration of study medication.

Patients treated with rituximab may receive non-live vaccinations. However, response rates to non-live vaccines may be reduced. In a randomized study of immunization responses, patients with RA, treated with rituximab and methotrexate, had comparable response rates to tetanus recall antigen (39% vs. 42%), reduced rates to pneumococcal polysaccharide vaccine (43% vs. 82% to at least two pneumococcal antibody serotypes), and keyhole limpet hemocyanin (KLH) neoantigen (47% vs. 93%), when given at least 6 months after rituximab, compared with patients receiving only methotrexate (Bingham et al. 2010).

In the overall experience of rituximab repeat treatment in RA patients over 1 year, the proportions of patients with positive antibody titers against *S. pneumoniae*, influenza, mumps, rubella, varicella, and tetanus toxoid were generally similar to the proportions at baseline.

Patients who have been treated with a live or attenuated vaccine within 28 days prior to randomization will be excluded from study participation.

The use of live or attenuated vaccines (i.e., measles, mumps, rubella, oral polio, BCG, typhoid, yellow fever, vaccinia, some forms of influenza [e.g., FluMist], or any other live vaccines not yet licensed but belonging to this category) are specifically prohibited during the study and while the patient's peripheral B cells are depleted.

The use of killed or inactivated vaccine (e.g., some forms of influenza) is not prohibited during the study; however, the efficacy of certain vaccines during or following periods of B-cell depletion has not been studied.

Patients who are eligible for yearly influenza vaccine or who require other non-live booster vaccinations can receive vaccination with killed/toxoid vaccines consistent with normal clinical practice.

Rituximab—F. Hoffmann-La Roche Ltd
63/Protocol WA29330, Version 5

5.1.1.8 Pregnancy

A reproductive toxicology study was conducted in cynomolgus monkeys to investigate the effects of rituximab on embryo-fetal development. Doses up to 100 mg/kg were administered weekly during the period of organogenesis. There were no findings of toxicity to the dams or the developing fetuses, and the only effect noted was the dose-dependent pharmacologic depletion of peripheral CD19+ B cells in the lymphoid organs of the fetuses.

Studies of the human reproduction have not been performed. It is not known whether rituximab can cause fetal harm when administered to pregnant women or whether it can affect reproductive capacity. However, since IgG molecules such as rituximab are known to cross the placenta, rituximab may cause fetal CD19+ B-cell depletion. Transient B-cell depletion and lymphocytopenia have been reported in some infants born to mothers exposed to rituximab during pregnancy. It is not known whether rituximab is excreted in breast milk and what effect this might have on the breast-feeding infant. However, since immunoglobulins are found in breast milk, breast-feeding mothers are excluded from participation in the study.

Well-controlled reproductive studies with glucocorticoids have not been performed in humans, but high doses of glucocorticoids given during pregnancy have caused hypoadrenalism in newborns.

Female patients should avoid becoming pregnant during this study, including the SFU period. As such, women of childbearing potential should use two effective methods of contraception, including at least one method with a failure rate of <1% per year, for the duration of the study and for 1 year after receiving rituximab. Regular pregnancy tests will be performed per the schedule of assessments ([Appendix 1](#)).

Patients who become pregnant will not receive additional doses of rituximab or MMF while pregnant or breast-feeding. Pregnancies occurring during the entire study (including the SFU period) must also be reported to the investigator. The investigator should counsel the patient, and discuss the risks of continuing with the pregnancy and the possible effects on the fetus. Monitoring of the patient should continue until conclusion of the pregnancy.

Effects on pregnancies in partners of male patients whose peripheral CD19+ B cells are depleted have not been studied. Therefore, it is strongly advised that male patients also use reliable contraception while receiving rituximab in this trial and for 1 year after receiving rituximab.

5.1.1.9 Management of Specific Adverse Events Infusion-Related Reactions

In the event of a mild infusion-related reaction, the infusion rate should be reduced to half the current rate (e.g., from 100 mg/hr to 50 mg/hr). Once the adverse event has

Rituximab—F. Hoffmann-La Roche Ltd
64/Protocol WA29330, Version 5

resolved, the infusion must continue at the reduced rate for an additional 30 minutes. If tolerated, the infusion rate may be increased to the next highest rate on the infusion schedule. Patients who experience a moderate to severe infusion-related reaction (e.g., fever > 38.5°C, chills, mucosal swelling, or systolic blood pressure decrease of > 30 mmHg) should have their infusion interrupted immediately and should receive aggressive symptomatic treatment. After all symptoms have resolved, the infusion may be restarted at half the previous rate. If the patient tolerates the reduced rate for 30 minutes, the infusion rate may be increased to the next highest rate following the infusion schedule. Patients who experience a Grade 4 (life-threatening) event during an infusion should have their infusion stopped. Additional infusions should not be given.

Additional instructions pertaining to the rituximab infusion are provided in [Appendix 3](#).

Infections

Rituximab (or matching placebo) should not be administered in the setting of an active infection. If a patient experiences a new infection between the Day 1 and Day 15 infusions of any course, the Day 15 infusion should be delayed (up to a maximum of 28 days from the scheduled Day 1 date) until the infection has completely resolved and treatment with any anti-infective medications has been completed. This will not affect the patient's eligibility to receive additional courses of treatment as required. However, repeat infusions of rituximab (or matching placebo) should only be considered once any infection, experienced at any time during the study, has fully resolved.

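### For an infection between the two infusions of a course, Protocol Sections 5.1.1.9 and 4.6.4 set different conditions for the second infusion, with no precedence stated, and on some dates both cannot be met

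*Protocol*

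**What the plan says.** Protocol Section 4.3.2.1 sends sites to Section 4.6.4, Section 5.1.1.9 and Appendix 3 for dose modification and interruption, without ranking them. It also makes the Day 168 and Day 182 infusions conditional on the safety criteria in Section 4.6.4.

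Section 5.1.1.9 opens its infection rule with "If a patient experiences a new infection between the Day 1 and Day 15 infusions of any course". The second infusion then "should be delayed (up to a maximum of 28 days from the scheduled Day 1 date) until the infection has completely resolved"; a second condition is that all anti-infective treatment is finished. No waiting period follows completion. The section adds that such a delay does not affect eligibility for further courses, and that repeat infusions "should only be considered once any infection, experienced at any time during the study, has fully resolved".

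Section 4.6.4 begins with a hold for medically significant Grade 3 or 4 infection: "no further doses of rituximab/placebo or MMF/placebo study drug treatment should be provided until the infection has resolved". It then lists criteria, introduced as additional to what precedes them, that are mandatory before either study drug is resumed. Among them, the patient must have had no active infection (fungal nail-bed infection excepted), and no major episode of infection requiring hospitalization or "treatment with IV anti-infectives within 4 weeks prior to infusion". A further clause, joined by *and*, refers to "completion of oral anti-infectives within 2 weeks prior to infusion". Section 4.6.4 gives no maximum delay.

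**The concern.** A site with a patient who had an infection between two infusions is pointed to two sections that release the second infusion on different dates. Section 5.1.1.9 looks only at whether the infection and its treatment are over, and it stops the clock at 28 days. Section 4.6.4 counts 2 or 4 weeks back from the infusion and does not stop the clock.

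Infection is a named risk of rituximab (Section 5.1.1.3) and of MMF (Section 5.1.2). If sites read the sections differently, one may infuse a recently treated patient whom another would hold back. Whether a rituximab patient receives one or two infusions in a course could also depend on the section consulted. The SAP summarizes infusions and dose received (Sections 4.3 and 4.9.1) and infections (Section 4.9.2), so site interpretation would enter both summaries.

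**Working it through.** The plan states no figure to reproduce; the check is day arithmetic on the two rules.

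**Inputs**

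| | Section 5.1.1.9 | Section 4.6.4 |
|---|---|---|
| Covers | new infection between the two infusions of any course | resumption of either study drug; Days 168 and 182 named in Section 4.3.2.1 |
| Wait after oral anti-infectives | none | 14 days |
| Wait after IV anti-infectives or hospitalization | none | 28 days |
| Limit on delay | 28 days from the course's scheduled first infusion | none |

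**Formulas.** Let *e* be the day anti-infective treatment (or hospitalization) ends, with the infection resolved by then, and *s* the scheduled day of the second infusion. The earliest permitted day is:
- Section 5.1.1.9: max(*s*, *e*)
- Section 4.6.4, oral: max(*s*, *e* + 14)
- Section 4.6.4, IV or hospitalization: max(*s*, *e* + 28)

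The limit *L* is the scheduled first infusion day + 28.

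**Second course** (*s* = 182, *L* = 168 + 28 = 196)

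| Event | 5.1.1.9 alone | 4.6.4 | By Day 196? |
|---|---|---|---|
| Oral course completed Day 178 | 182 | 178 + 14 = 192 | yes, 10 days later |
| Oral course completed Day 182 | 182 | 182 + 14 = 196 | yes, on the last day |
| Oral course completed Day 183 | 183 | 183 + 14 = 197 | no |
| Last IV anti-infective Day 169 | 182 | 169 + 28 = 197 | no |
| Last IV anti-infective Day 177 | 182 | 177 + 28 = 205 | no |

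Both rules can be met only if *e* + 14 ≤ 196, that is *e* ≤ 182, for oral treatment. For IV treatment or hospitalization, *e* + 28 ≤ 196 requires *e* ≤ 168, the day of the first infusion itself. So an infection between the infusions that needs IV treatment or hospitalization on Day 169 or later cannot satisfy both.

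**First course** (*s* = 15, *L* = 1 + 28 = 29), if Section 4.6.4 applies to it
- Oral course completed Day 14: Day 15 against 14 + 14 = Day 28.
- Oral course completed Day 16: Day 16 against 16 + 14 = Day 30, past the limit.
- Last IV anti-infective Day 10: Day 15 against 10 + 28 = Day 38, past the limit.

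**Counting conventions.** Day *e* + 14 (or *e* + 28) is taken as the first day outside the washout. If the first infusion day is itself counted as the first of the 28 days, the limits become Day 195 and Day 28. The cut-offs then move one day earlier, and no IV-treated or hospitalized case fits.

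**The case against.** The strongest reply is that Section 5.1.1.9 states a necessary condition, not a permission. It says when to delay; it does not say a patient may be infused with the Section 4.6.4 criteria unmet. A site sent to both sections should apply both. For starting a later course (Day 168) this stands: the sentence on repeat infusions is compatible with stricter criteria, and Section 5.1.1.3 repeats it with a pointer to Section 4.6.4. It does not dispose of the second infusion. The delay sentence carries no such pointer, and applying both rules often makes the delayed infusion impossible inside the window that Section 5.1.1.9 provides for it.

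A second reply is that the Section 4.6.4 list governs only resumption, so Section 5.1.1.9 is the specific rule for first-course Day 15. That is arguable: Section 4.3.2.1 ties only Days 168 and 182 to the criteria, and Day 15 falls under them only if a delayed infusion counts as resuming treatment. The reply fails for Day 182, which both sections cover.

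A third is that the oral clause in Section 4.6.4 is joined by *and*, so it may not be a bar in its own right. The parallel exclusion criterion in Section 4.1.2 uses *or*, which supports reading it as separate. The oral examples depend on that reading; the IV and hospitalization examples do not.

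A reader might also infer a third competing rule from the Grade 3–4 hold. The documents do not support this: the criteria are expressly additional to the hold, so the two are cumulative.

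**Conclusion.** The inconsistency stands for the second infusion of a course. It is explicit for Day 182 and conditional for first-course Day 15. An oral course completed from Day 169 to Day 182 moves the earliest second-course infusion date under Section 4.6.4 later than under Section 5.1.1.9 but still inside the limit. Completion on Day 183 or later, or IV treatment or hospitalization on Day 169 or later, leaves no date that satisfies both. These figures assume the counting convention shown and, for oral treatment, that the clause is a separate bar.

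A reader might infer that the infusion is then permanently lost. The documents do not say so: none states what happens after the limit. Section 6 of the Protocol says only that patients who miss doses stay in the study and continue study drug. A reader might also want a number of patients affected; the documents give no infection rate from which to derive one. Patients who are neither hospitalized nor given anti-infectives meet no washout conflict. The consequence for active rituximab dosing concerns the rituximab arm only, because the infusion in the MMF arm is placebo. Sample size, power and the planned analyses are unchanged. The matter is a wording inconsistency in a safety rule and should be corrected.

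**What to change.** Reconcile Sections 4.6.4 and 5.1.1.9 into one condition for giving the second infusion of a course after an infection, and cross-refer to it from the other places (Sections 4.3.2.1 and 5.1.1.3). The text should:
- state whether the condition covers first-course Day 15 as well as Day 182;
- make clear whether the oral anti-infective clause is a separate bar;
- make the 28-day limit and any washout consistent with each other;
- state what happens to the infusion when they cannot both be met.

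The sponsor's clinical team decides which condition stands. The cost is protocol wording and a letter to sites; no visit, test or patient is added.
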